## 11.6 Patient Deaths

Every effort should be made to provide a copy of the death summary, and autopsy report as applicable, to the Sponsor. The Sponsor may also request additional information to support the cause of death (e.g. last available medical consult, echo report).

## 11.7 Sponsor Assessment and Reporting

The Sponsor is responsible for the classification and reporting of adverse events and ongoing safety evaluation of the clinical investigation in accordance with 21 CFR 812.

All AEs will be reviewed by the Sponsor's Clinical Safety department. Each AE will be assessed for seriousness, device and procedure relatedness, and whether it was anticipated or not anticipated (based on the list of potential risks provided in section 3.1). In case of disagreement between the Sponsor or CEC and the Investigator, the Sponsor will communicate both opinions to concerned parties, as necessary.

A summary of adverse events will be reported to the FDA annually in the Annual Progress Report (APR).

The Sponsor will also report any confirmed unanticipated adverse device effect (UADE) to FDA as soon as possible, but no later than 10 working days after first receiving notice of the effect.

## 11.8 Investigational Device Explants

An Edwards' study device that is explanted at any time with an allegation of device malfunction or deficiency, should be returned to the Sponsor for evaluation. All other explants should be discarded.

Once the study device is explanted, the patient is followed for 30 days after the explant, unless there is an ongoing related adverse event and its outcome is not deemed resolved by the Investigator. Patients will then be exited from the study once AE(s) resolved or 180 days post-explant, whichever comes first. Return kits for explanted devices will be provided upon request by the clinical monitor or study team.

## 11.9 Investigational Device Observations and Deficiencies

All suspected device observations and deficiencies (i.e. malfunctions, use errors resulting in device malfunction, inadequate labelling) will be documented on an individual device observation and deficiency form or equivalent.

In the event of a suspected deficiency or other device issue, the device shall be returned to the Sponsor, to the extent possible, for analysis. Instructions for returning the investigational device will be provided by the Sponsor.

## 12 STATISTICAL ANALYSIS

### 12.1 Sample Size

This clinical study will enroll up to 65 patients (pending FDA approval). [REDACTED]

### 12.2 Analysis Populations

#### 12.2.1 Intention-to-Treat (ITT) Population

The intention-to-treat (ITT) population includes all patients who signed informed consent, met eligibility criteria, and in whom the study procedure has been attempted (i.e. skin incision to introduce the PASCAL System).

The ITT population will be used for performance endpoints and safety analysis.

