## 7.2 Inclusion Criteria

Patients enrolled must meet ALL of the following criteria:

1. Age  $\geq 18$  years old
2. Symptomatic despite optimal medical therapy per local Heart Team
3. Functional or degenerative TR graded as severe\* as assessed by the echo core lab
4. The local site Heart Team determines that the patient is appropriate for transcatheter tricuspid valve repair
5. Patient is willing and able to comply with all specified study evaluations and provides written informed consent.

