### **12.2.2 As-Treated (Implanted) Population**

The as-treated (implanted) population is a subset of the ITT population and includes all patients in whom the study device is implanted and remains in position at the time of the patient's exit from the procedure room.

The as-treated (implanted) population will be the primary analysis population for performance and additional safety assessment.

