### **12.2.3 Per-protocol (PP) Population**

The per-protocol (PP) population is a subset of as-treated (implanted) population in whom there are no major inclusion/exclusion criteria-related deviations.

Additional analyses of performance and safety data using the PP population will be performed if there is a clinically meaningful difference from the as-treated population.

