### **13.2 Protocol Deviations and Medical Emergencies**

A protocol deviation is defined as an event where the Investigator or study personnel did not conduct the study according to the clinical protocol. Investigators shall be required to obtain approval from the Sponsor before initiating deviations from the study protocol, except where necessary to protect the life or physical well-being of a patient in an emergency. If an Investigator or designee contacts the Sponsor to obtain prior approval for a change to the clinical study requirements, the approval or disapproval will be documented in writing. A copy of the approval or disapproval will be forwarded to the Investigator and a copy will be maintained in the study files. Prior approval is generally not expected in situations where unforeseen circumstances are beyond the Investigator's control, (e.g. patient did not attend scheduled follow-up visit, etc.); however, the event is still considered a deviation.

Deviations shall be reported to the Sponsor regardless of whether medically justifiable, pre-approved by the Sponsor, or taken to protect the patient in an emergency. Patient-specific and non-patient specific deviations, (e.g. unauthorized use of an investigational device outside the study, unauthorized use of an investigational device by a physician who is not listed in the Delegation of Authority Log, etc.) will be reported to the Sponsor. Patient-specific deviation

information must be recorded directly on the Protocol Deviation eCRF and non-patient specific deviations will be documented. Investigators will also adhere to procedures for reporting study deviations to their IRB in accordance with their specific reporting policies and procedures.

A major protocol deviation or noncompliance is one that may have a significant impact on patient safety, well-being, the patient's willingness to participate in the study, or that may compromise the integrity of the study data and analysis, including:

- A. Patients implanted/treated with study device not having met eligibility criteria at the time of implant/treatment.
- B. Informed Consent not signed or signed after the initiation of non-standard of care, research related assessments.
- C. UADE not reported to IRB/Sponsor within the required timeframe
- D. Unauthorized use/implant of an investigational device

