4.2 As-Treated (Implanted) Population

 Edwards	Revision Date: January 22, 2019		Rev	For Use Only by Affiliates of Edwards Lifesciences	Page 13 of 25
	Title	Statistical Analysis Plan for Edwards CLASP TR EFS			

The as-treated (implanted) population is a subset of ITT population and includes all patients in whom the study device is implanted and remains in position at the time of the patient's exit from the procedure room.

The as-treated (implanted) population will be the primary analysis population for performance and additional safety assessment.

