4.3 Per-Protocol (PP) Population

The per-protocol (PP) population is a subset of as-treated (implanted) population in whom there are no major inclusion/exclusion criteria-related deviations.

Additional analyses of performance and safety data using the PP population will be performed if it is clinically meaningful in addition to the as-treated analysis.

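### The ITT definition requires that eligibility was met and the other two sets sit inside it, so on a literal reading a patient treated despite being ineligible is in no analysis set and drops out of the 30-day MAE and success rates

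*Protocol*

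**What the plan says.** Protocol 12.2.1 and SAP 4.1 give the same ITT definition: the population "includes all patients who signed informed consent, met eligibility criteria, and in whom the study procedure has been attempted". Attempted means a skin incision to introduce the device, which is also the point of enrollment in Protocol 8.4. Both sections assign ITT to the performance endpoints and the safety analysis.

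The other two sets are nested:

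- As-treated, in Protocol 12.2.2, "is a subset of the ITT population and includes all patients in whom the study device is implanted"; in SAP 4.2 it "is a subset of ITT population and includes all patients in whom the study device is implanted".
- Per-protocol is drawn from as-treated. Protocol 12.2.3 limits it to patients "in whom there are no major inclusion/exclusion criteria-related deviations", and SAP 4.3 sets the same condition, "no major inclusion/exclusion criteria-related deviations".

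SAP 8.1 reports the 30-day MAE composite and device, procedural and clinical success for ITT and as-treated only.

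Protocol 13.2 lists as major deviations, under item A, "Patients implanted/treated with study device not having met eligibility criteria at the time of implant/treatment" and, under item B, "Informed Consent not signed or signed after the initiation of non-standard of care, research related assessments". Consent is also part of inclusion criterion 5 in Protocol 7.2: "Patient is willing and able to comply with all specified study evaluations and provides written informed consent".

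The AE/SAE listing covers the whole study population in Protocol 5.3.3 and SAP 3.3.3, but the ITT population in Protocol 12.6 and SAP 8.1. The early/late AE summary in SAP 9.2 names no population.

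**The concern.** The ITT set should be the widest of the three, and here it is conditioned on eligibility. Because the others are built inside it, a patient who was treated but ineligible has no route into any set. That patient's MAE or failed procedure would be left out of the reported rates.

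The definitions also work against each other. The per-protocol rule exists to take eligibility deviations out of as-treated. If everyone in as-treated met eligibility, it has little or nothing to remove, and comparing the two sets can show little of what those deviations do.

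Two analysts could build different ITT sets from the same data. No hypothesis is tested, but these are the study's safety and performance rates, and guiding later study designs is one of its stated objectives.

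**Working it through.** The plan gives no figure to reproduce: the analysis is descriptive and the text after the sample size in Protocol 12.1 is redacted. The check is first one of set membership, then an illustration of size.

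**Step 1. Membership of patients with a skin incision, taking the definitions literally** (1 = in the set, 0 = not; order ITT / as-treated / per-protocol)

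| Eligible | Implanted | As written | Eligibility condition deleted |
|---|---|---|---|
| yes | yes | 1 / 1 / 1 | 1 / 1 / 1 |
| yes | no | 1 / 0 / 0 | 1 / 0 / 0 |
| no | yes | 0 / 0 / 0 | 1 / 1 / 0 |
| no | no | 0 / 0 / 0 | 1 / 0 / 0 |

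As written, per-protocol equals as-treated except for deviations compatible with the ITT wording. Late consent is a possible case: it touches inclusion criterion 5 and is a major deviation under 13.2 item B, yet the patient did sign and can still be in ITT.

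**Step 2. Size for the MAE rate.** N = 65 is the protocol's maximum. The 6 MAEs and the numbers of ineligible patients are assumptions; the documents give none. Intervals are 95% Clopper-Pearson, the method in SAP 6.1.

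- All treated: 6/65 = 9.2% (3.5 to 19.0).
- One dropped: 6/64 = 9.4% (3.5 to 19.3) if that patient had no MAE, or 5/64 = 7.8% (2.6 to 17.3) if there was one.
- Two dropped: 6/63 = 9.5% (3.6 to 19.6), 5/63 = 7.9% (2.6 to 17.6) or 4/63 = 6.3% (1.8 to 15.5), according to whether none, one or both had an MAE. The shifts are +0.3, -1.3 and -2.9 points.

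If ineligible patients have the same risk as the rest, the number of MAEs among the two dropped is hypergeometric:

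- P(0) = (59 × 58)/(65 × 64) = 82.3%
- P(1) = (2 × 6 × 59)/(65 × 64) = 17.0%
- P(2) = (6 × 5)/(65 × 64) = 0.7%

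The expected rate after dropping is 0.823 × 9.52% + 0.170 × 7.94% + 0.007 × 6.35% = 9.2%, unchanged.

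**Step 3. Size for procedural success**, assuming 55 successes in 65: 84.6% (73.5 to 92.4). With two dropped:

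- Both failures: 55/63 = 87.3% (76.5 to 94.4), shift +2.7 points, probability (10 × 9)/(65 × 64) = 2.2% at equal risk.
- One of each: 54/63 = 85.7% (74.6 to 93.3), shift +1.1 points, probability (2 × 55 × 10)/(65 × 64) = 26.4%.
- Both successes: 53/63 = 84.1% (72.7 to 92.1), shift -0.5 points, probability (55 × 54)/(65 × 64) = 71.4%.

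Device success is analyzed per device, so no patient-level figure is given for it.

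**Step 4. The SAP's own size.** SAP 2.2 still plans 15 patients. With 1 assumed MAE, 1/15 = 6.7% (0.2 to 31.9) becomes 0/14 = 0.0% (0.0 to 23.2) if the one dropped patient had the MAE, or 1/14 = 7.1% (0.2 to 33.9) if not.

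**The case against.** The strongest reply is that the eligibility condition refers to the decision taken before the procedure. Protocol 8.4 and the enrollment definition in Appendix A describe consent, a finding of eligibility and then skin incision, the same three elements in the same order as ITT. On that reading ITT is close to shorthand for all enrolled patients. Two other definitions fit it better: as-treated is said to include all implanted patients, which cannot hold if some of them lie outside ITT, and the per-protocol rule then has something to do. Item A of 13.2 specifies status at the time of treatment, a qualifier the ITT text lacks, so the contrast could support the screening reading. Core-laboratory assessment of several criteria and central screening (Protocol 3.2 and 14.3) should also make such patients uncommon.

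Much of this stands as evidence of intent. It does not settle the text. Neither ITT definition mentions a screening decision, and Protocol 13.2 uses the same idea for actual status at treatment. The poor fit with the as-treated and per-protocol wording shows that the definitions conflict; it does not return the patient to a set. Rarity limits the size of the effect, but the protocol itself foresees the case.

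On SAP 9.2 the objection is right that SAP 4.1 already makes ITT the default for safety analysis, so the missing population there is only a matter of detail.

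**Conclusion.** The point holds on the wording of both documents and should be fixed. If the stated rule is followed, a patient treated despite ineligibility is left out of the 30-day MAE, device, procedural and clinical success rates.

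The effect is likely small and its direction is unknown: under the assumed counts with 65 patients and two dropped, between -2.9 and +0.3 points for MAE and between -0.5 and +2.7 points for procedural success. Bias arises only if ineligible patients differ in risk from the rest. The true numbers of such patients and events cannot be derived from the documents.

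AE collection, sponsor review and DSMB oversight are not affected, and no loss of events from the AE/SAE listing is claimed. The inconsistent population for that listing is a separate, smaller matter.

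**What to change.** - Delete the eligibility condition from Protocol 12.2.1 and SAP 4.1, so that ITT is every consented patient with a skin incision to introduce the PASCAL System.
- Build as-treated from that set and let per-protocol remove the eligibility deviations.
- Use this ITT set for the MAE, success and AE analyses, with as-treated alongside as SAP 8.1 already plans.
- If eligibility as judged at screening was meant, say so in both ITT definitions and state that ineligibility found later does not remove a patient. This would also resolve the ambiguity.
- Give one population for the AE/SAE listing in Protocol 5.3.3 and 12.6 and SAP 3.3.3 and 8.1. Naming the population in SAP 9.2 would complete the text.

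The cost is one phrase deleted in each document, one aligned statement for the listing and one population named in SAP 9.2. No new data are needed. The reported rates may move slightly in either direction.

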### **12.2.2 As-Treated (Implanted) Population**

The as-treated (implanted) population is a subset of the ITT population and includes all patients in whom the study device is implanted and remains in position at the time of the patient's exit from the procedure room.

The as-treated (implanted) population will be the primary analysis population for performance and additional safety assessment.

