### 5.2.2 Procedural Success

Device success with evidence of a reduction in TR grade by at least one grade (scale: none/trace, mild, moderate, severe, massive, torrential\*9) at end of procedure, and without the need for a surgical or percutaneous intervention prior to hospital discharge. *Per patient analysis.*

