### 5.2.3 Clinical Success

Procedural success without MAEs at 30 days. *Per patient analysis.*

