## 7.4 Study Exit Criteria and Procedures

The reason for study exit will be documented on the appropriate case report forms and in the medical records for each patient who exits the study.

Patients may exit the study for any of the following reasons:

- Screen Failure
- Study Device Attempted But Not Implanted
  - Enrolled patients for whom the implant procedure was prematurely aborted (e.g., entered procedure room and anesthesia induced, but study procedure not attempted (i.e. skin incision to introduce the PASCAL System) or TTVr procedure attempted but did not receive a study device, will be followed for 30 days for safety evaluations only or until resolution of any adverse events related to the implant procedure and then exited from the study.
- Study Device Re-intervention/Explant
  - Patients who have a surgical re-intervention where the device is explanted will be followed for 30 days post-re-intervention for safety evaluations only or until resolution of any adverse events related to the re-intervention and then exited from the study. Patients who have a percutaneous re-intervention where the study device remains in place will continue to be followed for the duration of the study.
- Completion per Protocol
- Withdrawal
  - Patient Withdrawal: The patient may voluntarily withdraw from the clinical study at any time, without penalty or loss of benefits to which they are otherwise entitled.
  - Physician Withdrawal: The Investigator also has the right to withdraw a patient if s/he feels it is in the best interest of the patient to do so.
- Death
- Lost to Follow-up
  - If a patient cannot be reached for a follow-up visit, the Investigator will document the contact efforts made to the patient and/or effort to obtain hospital records in the appropriate electronic case report form. If the patient cannot be reached in any way, or misses a visit, the patient will be considered “unable to contact” for that time interval. After three (3) documented unsuccessful attempts to make contact prove unsuccessful, a certified letter will

be sent to the patient's residence. If there is no response after the certified letter is sent, the patient will be considered "lost to follow-up".

- For patients who are lost to follow-up or withdraw early, Sponsor may request the site to search the Social Security Death Index and/or other death registries and may request the site to obtain the death certificate, if applicable.

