6. STATISTICAL ANALYSIS

6.1 General Conventions

- For continuous variables, data will be summarized using the number of observations, mean, median, standard deviation, minimum, maximum, and 95% confidence intervals (based on normal distribution) per table shells. Nonparametric techniques may be used if the data

 Edwards Lifesciences	Revision Date: January 22, 2019		Rev 	For Use Only by Affiliates of Edwards Lifesciences	Page 15 of 25
	Title	Statistical Analysis Plan for Edwards CLASP TR EFS			

does not meet the assumptions of parametric tests.

- For categorical variables, data will be summarized using the number of observations, percentage, and 95% Clopper-Pearson confidence intervals per table shells. In general, the denominator for the percentage calculation will be based on total number of patients with evaluable data for a specified time point unless otherwise specified. Patients with missing data will be excluded from the denominator.
- For time-to-event variables, survival analysis will be used to analyze the data. Summaries will include the number of patients at risk, and number of patients with the event. Patients without events will be censored at their last known event-free time point. If this event-free time point occurs after the analysis time point, the days to event variable will be set equal to the analysis time point so that the patient will be included in the analysis. For patients who did not have an event or early withdrawal and have not yet completed the analysis visit, they will be censored at their last information date. Time to first event curves will be constructed using Kaplan-Meier estimates and all post procedure results will be summarized with Kaplan-Meier estimates of event rates. Hazard ratios, confidence interval for the hazard ratios, and p-values may also be presented from a Cox proportional hazards model.
- For selected variables, in addition to descriptive summary statistics at each follow-up assessment, change from baseline to subsequent time point will be summarized. Paired (i.e., patients with available data at both baseline and respective time point) and unpaired data will be presented separately for selected variables. In general, patients with missing baseline or following-up values will be excluded from the analysis unless otherwise specified.

 Edwards	Revision Date: January 22, 2019		Rev	 For Use Only by Affiliates of Edwards Lifesciences	Page 16 of 25

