6.2 Handling of Missing Data

All statistical analysis on the endpoints will be performed using only those patients with available data required for endpoint analysis. No missing value imputation will be performed unless otherwise specified.

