8. STATISTICAL ANALYSIS OF STUDY ENDPOINTS

8.1 Safety and Performance Endpoints

Safety:

The safety endpoint for this clinical study is a composite endpoint of Major Adverse Events (MAEs) at 30 days. No hypotheses testing will be performed for this endpoint. MAE endpoint and its components will be summarized by counts, percentage and 95% Confidence Interval (CI) of the percentage for the ITT and AT population. CEC adjudicated data will be used in the analysis.

Performance:

All performance endpoints will be summarized by counts and percentage.

The device success endpoint will be evaluate for the ITT and AT cohorts, per device analysis.

The procedure success endpoint will be assessed for the ITT and AT cohort, per patient analysis. Only device-related intervention will be considered when calculating procedure success.

The clinical success endpoint at 30 days will be summarized for the ITT and AT cohort, per patient analysis. CEC adjudicated data will be used for MAEs.

Additional Safety Assessments at 30 days will be summarized by counts and percentages for the ITT and AT cohort.

In addition to the above assessments, a listing of all the AEs and SAEs for the ITT study population will be provided.

 Edwards Lifesciences	Revision Date: January 22, 2019		Rev	For Use Only by Affiliates of Edwards Lifesciences	Page 22 of 25
	Title		Statistical Analysis Plan for Edwards CLASP TR EFS		

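### The implanted set is named primary for performance although being implanted is part of procedural and clinical success; the already planned ITT analysis should lead.

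*Protocol*

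**What the plan says.** Protocol 12.2.2 defines the AT set as the ITT patients whose device is implanted and still in place when they leave the procedure room, and continues: "The as-treated (implanted) population will be the primary analysis population for performance and additional safety assessment". SAP 4.2 repeats the sentence. Protocol 12.2.1 defines ITT as consented, eligible patients in whom the skin incision was made, and says of it: "The ITT population will be used for performance endpoints and safety analysis". SAP 4.1 agrees. Neither document says how that use of ITT ranks against a primary AT set, and neither gives a reason for choosing AT.

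The endpoints are nested. Device success (Protocol 5.2.1, per device) is intended deployment plus intended retrieval of the delivery system, judged when the patient leaves the catheterization laboratory. Procedural success (5.2.2, per patient) begins "Device success with evidence of a reduction in TR grade by at least one grade" and also requires no intervention before discharge. Clinical success (5.2.3, per patient) is "Procedural success without MAEs at 30 days".

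SAP 8.1 plans both sets, for example "The procedure success endpoint will be assessed for the ITT and AT cohort, per patient analysis", and does the same for device and clinical success. Protocol 7.4 provides for patients with a "TTVr procedure attempted but did not receive a study device, will be followed for 30 days for safety evaluations only" or until related adverse events resolve.

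**The concern.** Entry to the AT set depends on how the procedure turned out, and that outcome is itself a necessary part of procedural and clinical success. An attempt that ends without an implant is one of the main ways the system can fail to perform. The analysis labelled primary takes those failures out of the denominator, so its rate can equal the ITT rate or exceed it, but never fall below it.

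The study's objectives include evaluating performance and guiding the design of later studies. A planner needs the proportion of attempted patients who succeed. If the rate labelled primary is the one carried forward, a later study would start from too high a figure whenever any attempt ends without an implant.

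A smaller gap lies beside this one. SAP 6.1 says "Patients with missing data will be excluded from the denominator", and SAP 6.2 analyses endpoints "using only those patients with available data required for endpoint analysis". A non-implanted patient may have no end-of-procedure TR grade. Read literally, these rules could drop that patient from the ITT rate too, although failure is already known.

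**Working it through.** There is no planned rate, power or performance goal to reproduce: Protocol 12.3 and 12.4.2 are descriptive. The check is of the denominator.

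**Inputs.** N = up to 65 (Protocol 12.1). The SAP, written to protocol version A, says 15 (SAP 2.2). k, the number attempted but not implanted, and the success rate among the implanted are assumptions. The interval method is 95% Clopper-Pearson (SAP 6.1).

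**Formulas.** Let x be the number of patients with success. A non-implanted patient cannot be a success, so all x are in the AT set:

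- AT rate = x/(N−k)
- ITT rate = x/N
- AT/ITT = N/(N−k)
- AT − ITT = AT rate × k/N

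**N = 65, x = 90% of (N−k), rounded to a whole patient:**

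| k | AT (95% CI) | ITT (95% CI) | Gap, points | Factor |
|---|---|---|---|---|
| 0 | 58/65 = 89.2% (79.1–95.6) | 58/65 = 89.2% (79.1–95.6) | 0 | 1.00 |
| 1 | 58/64 = 90.6% (80.7–96.5) | 58/65 = 89.2% (79.1–95.6) | 1.4 | 65/64 = 1.02 |
| 3 | 56/62 = 90.3% (80.1–96.4) | 56/65 = 86.2% (75.3–93.5) | 4.2 | 65/62 = 1.05 |
| 6 | 53/59 = 89.8% (79.2–96.2) | 53/65 = 81.5% (70.0–90.1) | 8.3 | 65/59 = 1.10 |
| 11 | 49/54 = 90.7% (79.7–96.9) | 49/65 = 75.4% (63.1–85.2) | 15.4 | 65/54 = 1.20 |

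**Sensitivity to the assumed success rate, k = 6.** At about 80%: 47/59 = 79.7% against 47/65 = 72.3%, gap 7.4 points. At about 95%: 56/59 = 94.9% against 56/65 = 86.2%, gap 8.8 points. The gap depends mainly on k.

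**N = 15.** k = 1: 13/14 = 92.9% against 13/15 = 86.7%, gap 6.2 points. k = 2: 12/13 = 92.3% against 12/15 = 80.0%, gap 12.3 points.

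**Device success** is counted per device. Devices tried in patients who left without an implant drop out of AT, so the direction is the same. The size depends on the number of devices tried per patient, which the plan does not give, so no figure is offered.

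**The case against.** The strongest reply is that nothing is hidden. SAP 8.1 reports all three endpoints in both sets, performance is summarized by counts and percentages, and no test or goal hangs on the primary label. That stands, and it limits the harm to the headline rate. It does not justify the label, which is the only ranking in either document and favours AT.

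A second reply is that the text is merely ambiguous: ITT may be meant for the three named endpoints and AT for performance data more widely. But the AT sentence says primary for performance without that limit. Even on this reading the two sentences need reconciling.

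Third, AT does not guarantee success. Failed retrieval, no grade reduction, an intervention before discharge and a 30-day MAE still count as failures there. This is correct; one route to failure is removed, not all.

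Fourth, a device deployed as intended that moves before the patient leaves would be outside AT without clearly failing device success as worded. This is a marginal case, since device success is itself judged on leaving the laboratory. The certainty claimed here is for patients with no implant.

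Fifth, every value of k is assumed. Text on prior tricuspid experience and on sample size is redacted, so an implant rate may exist there. At k = 1 the gap of 1.4 points is small beside an interval about 16 points wide (80.7 to 96.5). That is fair as to size. The direction is still fixed, and the AT interval makes no allowance for the excluded failures.

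Finally, ITT as defined requires eligibility to have been met, so it is the set of eligible attempted patients and not everyone enrolled at skin incision. Leading with ITT does not change that.

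**Conclusion.** The point holds. For procedural and clinical success, the analysis called primary leaves out attempted patients without an implant, who are certain failures and whom Protocol 7.4 foresees. Its rate is N/(N−k) times the ITT rate. With 65 patients and about 90% success among the implanted, that is nothing at k = 0, about 4 points at k = 3, 8 at k = 6 and 15 at k = 11. These sizes rest on assumed values of k and of the success rate; the direction does not. The effect is on the headline estimate only. The 30-day MAE endpoint is not affected, because ITT is already assigned to safety. This should be fixed, and both analyses needed are already planned.

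**What to change.** - **Protocol 12.2.1–12.2.2 and SAP 4.1–4.2:** name ITT, as defined in 12.2.1, as the primary population for device, procedural and clinical success. Keep AT as supportive for these endpoints and for follow-up echocardiographic and functional change.
- **SAP 8.1:** add that a patient with any known failed component, such as no implant, stays in the denominator as a failure even if the end-of-procedure TR grade or the 30-day visit is missing. Patients with no known failure but an incomplete assessment would still drop out under the available-data rule, so report their number beside the rate.

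The cost is wording in these sections, with the written amendment that Protocol 15.7 requires for the protocol part. No new data or analyses are needed. The headline success rates may be somewhat lower.
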